4.6.1 Early Termination Study Visit

Any participant who withdraws will be contacted by [name] to assess their desired level of participation. A final assessment visit with compensation will be offered to those who are willing to ensure we collect data about why the intervention or protocol did not meet their needs. Participants will have the right to decline this visit if they desire.

5 STUDY EVALUATIONS AND MEASUREMENTS**5.1 Screening and Monitoring Evaluations and Measurements**

Our pre-consent phone screening (included in data collection materials) will closely parallel the phone screening used by [name] in a prior, similar study (HSR#17-4351). This was efficient and well-tolerated by participants in that study. The primary goal will be to ensure eligibility and interest in study participation.

During the baseline and final assessment visits, study staff will read questionnaire items out loud to participants and record information directly into REDCap. See our Assessment Table for a list of all measures.

5.2 Efficacy Evaluations

Efficacy is not the intended goal of this treatment development study. However, eventually the goal will be to impact patient CV health. The primary behavioral target to achieve this impact will be Life Essential 8 CV health composite measure. We will also examine specific behavior change for targeted health behaviors (e.g., Both of these endpoints will be measured, as detailed above, at the baseline and 12-week assessment visits during this single arm pilot.

5.3 Pharmacokinetic Evaluation *Not applicable***5.4 Safety Evaluation**

Participant safety will be monitored by adverse events and rates of early termination of the study. We will also follow safety protocols in case we identify dangerous blood pressure, blood sugar, or heart rate values at baseline or final assessment visits. See Section 8 for details.

6 STATISTICAL CONSIDERATIONS

6.1 Primary Endpoint

Primary outcomes The primary endpoint of this study is the feasibility and acceptability of the program to participants in this treatment development phase. We will assess this by measuring our ability to recruit and retain participants, the dose of treatment we can deliver (i.e., participant's attendance and follow-up with scheduled sessions and treatment activities), and participants' report of their satisfaction and overall experience during participation in a structured survey (CSQ-8) and qualitative post-treatment interview. Secondary outcomes will include measures we plan to use in a future randomized pilot study (see Assessment Table).

Clinical Outcomes will occur at baseline and post-treatment. Our primary target is a composite measure of cardiovascular health developed by the American Heart Association, Life's Essential 8 (see Table 2).¹⁸ All biometric data and self-reported items will be collected and stored in REDCap.

6.2 Statistical Methods

6.2.1 Baseline Data

Baseline and demographic characteristics will be summarized by standard descriptive summaries (e.g. means and standard deviations for continuous variables such as age and percentages for categorical variables such as gender). We will also collect data using the Discrimination in Medical Settings scale, which has been piloted in previous and current work (D-HOMES; D-HOMES-Spanish).¹⁶

6.2.2 Efficacy Analysis

The primary purpose of this study is feasibility and acceptability. This will be assessed using the following data:

Qualitative data Analysis of audio recordings of post-treatment interviews will be completed by listening to files and taking detailed notes to highlight satisfaction, treatment experience, and suggested changes of intervention participants.

Survey data from the Client Satisfaction Questionnaire (CSQ-8) will be summarized using descriptive statistics. Exploratory analyses by race and gender will be done to look for any patterns.

Communication and treatment contact data will also be examined by creating summary counts of the number and types of communication (by modality and initiator), total minutes of completed treatment, and any notes from treatment sessions.

6.2.3 Pharmacokinetic Analysis *Not applicable.*

6.2.4 Safety Analysis *Not applicable since there is no control group in this study.*

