Key Criteria for Inclusion and Exclusion:	(1) Moderate to high CV risk defined as self-reported diagnoses by a medical professional of high blood pressure, high cholesterol, prediabetes, type 2 diabetes, or heart disease. (2) Experience of homelessness per the HEARTH Act which includes living in a supported housing facility (2011). (3) English-speaking, (4) and willingness to engage in coaching about changes to ≥1 health behavior related to cardiac risk that align with patients' personal CV risk behaviors. Medical diagnoses and medications will be confirmed in medical records after enrollment.
	Patient exclusion criteria will include conditions raising risk for coercion or limitation of capacity to ethically consent to research: (1) active intoxication, (2) active psychosis or dementia, (3) active legal commitment (per search of publicly available civil court records) or (4) pregnancy or lactation. This is aligned with previous studies by this team (K23DK118117).
	We will further confirm capacity to consent using a brief quiz (see attachments).
Number Of Participants	Total Number of Participants: 8

	
Total Number at Hennepin Healthcare: 8
 
Total Number of Sites: 1

Study Duration	
Each participant will be enrolled for 16 weeks.
 
The entire study is expected to last one year.

Study Phases	(1) Screening : screening for eligibility and obtaining consent, baseline assessment
Screening	(2) Intervention : study intervention with counselor support approximately weekly in-person and/or by phone x 12 weeks
Intervention	
Follow-Up	(3) Follow-up : final assessment
Efficacy Evaluations	
 • Cardiovascular health as measured by the American Heart Association's Life's Essential 8 score.¹⁸ This includes: 
 ○ Self-reported cardiovascular health behaviors (eating better, being more active, taking medications as prescribed, quitting tobacco, getting healthy sleep) ○ Blood pressure and body mass index (height, weight) ○ Cholesterol and Hemoglobin A1c measured by point-of-care fingerstick or venous blood draw ○ Skin carotenoid measurement by VEGGIE METER • Self-reported medication adherence • Self-reported psychological wellness • Self-reported drug and alcohol use • Self-reported health care use
Safety Evaluations	Not applicable in this single arm trial

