8.2 Adverse Event Reporting

Unanticipated problems related to the research involving risks to participants or others that occur during this study and SAEs will be reported to the IRB in accordance with IRB Prompt Reporting Guidelines. AEs that are not serious but that are notable and could involve risks to Participants will be summarized and submitted to the IRB at the time of continuing review.

[name] will be responsible for completing Adverse Events Forms should an event occur. She will report Serious Adverse Events to the HHRI IRB within 24 hours of having received notice of the event.

[name] will collaboratively gather any information needed to investigate the event and determine subsequent action. Any subsequent action will be documented and reported to the HHRI IRB and/or C2DREAM grant leaders and/or the Program Officer at NIH.

Adverse event reports will be reviewed annually with the HHRI IRB to ensure participant safety.

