8.4 Medical Emergencies

If non-urgent psychological distress arises in participants during study related activities, study staff will provide a handout about local mental health resources, including a 24-hour support line, behavioral health walk-in center, and psychiatric emergency room. If non-urgent physical health needs arise in participants, study staff will provide written resources about health care available through Health Care for the Homeless and Hennepin Healthcare. If staff identify that a participant has a high A1c or high cholesterol level, they will encourage the participant to visit their primary care physician or provide a resource sheet so that the participant can select a clinic to visit. If a participant wants to use nicotine patches to quit smoking, coaches will educate the participant on proper use of the patch and symptoms to be aware of such as skin irritation, dizziness, rapid heartbeat, or upset stomach that may arise if a person smokes while using the patch. Coaches will

encourage participants to reach out to their primary care provider or regular clinic prior to using the patch if they have any concerns or significant comorbidities and if they experience symptoms such as chest pain or if they become pregnant.

If an emergency physical or behavioral health situation arises, study staff will arrange for immediate clinical support from PI ([name]), Health Care for the Homeless clinical staff (who have a walk-in treatment model), the Hennepin County mental health crisis team (COPE Line, available by phone or in-person 24hrs./day, 7 days/week), or emergency medical services as appropriate. In the case of suicidal ideation, study staff will use the SI Questionnaire to guide their approach to working with the participant and reach out to [name] for support. These events will be written up and reviewed by the PI ([name]) and primary mentor ([name]) within 48 hours of the event and reported to the IRB if needed.

If measured blood pressure surpasses SBP>180 or DBP>100 or pulse>150 or if blood sugar measurement takes place within a study visit and falls <60 or >400/error, study staff will page [name] who will provide clinical assessment of symptoms and make referral or arrangement for immediate transfer to appropriate treatment as needed.

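### Section 6.2.4 rules out a safety analysis for lack of a control group; the reason is invalid, conflicts with Section 5.4, and leaves no descriptive safety summary planned as a study result

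*Combined protocol and SAP*

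**What the plan says.** - **Section 6.2.4 (Safety Analysis)**, in full: "Not applicable since there is no control group in this study".
- **Synopsis, Safety Evaluations row:** "Not applicable in this single arm trial".
- **Section 5.4 (Safety Evaluation):** "Participant safety will be monitored by adverse events and rates of early termination of the study". It continues: "We will also follow safety protocols in case we identify dangerous blood pressure, blood sugar, or heart rate values at baseline or final assessment visits".
- **Section 8.2 (Adverse Event Reporting):** "AEs that are not serious but that are notable and could involve risks to Participants will be summarized and submitted to the IRB", at continuing review. Serious AEs (SAEs) go to the IRB within 24 hours of notice. It adds: "Adverse event reports will be reviewed annually with the HHRI IRB to ensure participant safety".
- **Section 8.4 (Medical Emergencies)** sets alert limits for blood pressure, pulse and blood sugar. When one is crossed, staff page a study clinician, who assesses the participant and will "make referral or arrangement for immediate transfer to appropriate treatment as needed". No count or summary of these referrals is mentioned.
- **Sections 1.3, 2.1 and 6.1** make retention part of the primary outcome. Section 1.3 measures it by assessment visits and coaching sessions attended.

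**The concern.** Section 6.2.4 is not silent on safety. It states a rule and gives a reason, and the reason does not support the rule. Having no comparator prevents attribution and comparison; it does not prevent counting.

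If the statistical section is followed as written, the study's own results need contain no AE or SAE summary, although Section 5.4 says these are what safety will be judged on. The protocol itself foresees possible harms. Participants working on quitting smoking may receive nicotine lozenges or patches (Sections 4.2 and 7). All participants enter with a cardiovascular or metabolic diagnosis (Section 3.5.1). Section 9.4.2 lists patch reactions and allows that mental illness may worsen. The stated next step is a randomised pilot, whose designers would want event counts with a denominator.

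**Working it through.** **1. Is the reason valid?** Section 6.2.1 plans means, standard deviations and percentages for baseline data. Section 6.2.2 plans descriptive statistics for the satisfaction questionnaire (CSQ-8), counts of contacts by type and initiator, and total treatment minutes. All are single-arm summaries. A proportion x/N needs only the arm's own numerator and denominator, so the same treatment is open to AEs. Only safety is refused it.

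**2. Do the sections agree?** Section 5.4 names a rate (early termination) and AEs as safety measures. Section 6.2.4 says no safety analysis applies. The synopsis says no safety evaluation applies, while its data and safety monitoring row promises a detailed safety monitoring plan. These statements cannot all stand.

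**3. What is summarised, and where?**

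| Item | Summary the plan provides | What is missing |
|---|---|---|
| Non-serious AEs | Notable ones summarised for the IRB (8.2) | Events and participants affected, with N, as a study result |
| SAEs | Individual IRB reports; AE reports reviewed yearly with the IRB (8.2) | Same |
| Early terminations | Surface through retention and attendance (1.3, 6.1) | Tabulation by reason |
| Alert-value referrals | None stated | Any count |

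On the third row: Section 4.6 lets the investigator discontinue a participant for poor adherence or for AEs. An attendance count cannot tell these exits apart. Section 4.6.1 seeks reasons from people who withdraw and accept a final visit, but no table of reasons is planned.

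**4. What could eight participants show?** The plan states no safety rate, threshold or power, so there is no figure of its own to reproduce. The one input is N = 8 (synopsis; Section 3.3.2). Exact Clopper-Pearson 95% limits for x of 8 are the 2.5% quantile of Beta(x, 9 − x) and the 97.5% quantile of Beta(x + 1, 8 − x).

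- 0/8: the lower limit is 0; the upper limit is 1 − 0.025^(1/8) = 1 − 0.6306 = 36.9%. The one-sided 95% upper limit is 1 − 0.05^(1/8) = 31.2%.
- 1/8 = 12.5%: 0.3% to 52.7%.
- 2/8 = 25%: 3.2% to 65.1%.
- 3/8 = 37.5%: 8.5% to 75.5%.

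The summary can be computed, but the intervals are wide.

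**The case against.** The best defence is that oversight is already in place. Section 8.2 commits to an IRB summary of notable non-serious AEs, rapid SAE reports and annual review. Section 9.4.1 adds regular discussion of AEs, review of patient-safety issues by clinicians outside the study, and a description of the study as minimal risk. Nicotine products go only to participants who choose to work on quitting, as a first supply worth up to $20, with education on symptoms (Sections 7 and 8.4). With eight people, an interval reaching 36.9% after no events tells the reader little.

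Much of this stands, and it rules out two stronger readings that a reader might infer.

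- **That the safety data would never be summarised.** Section 8.2 contradicts this for notable non-serious AEs. It is true only of alert-value referrals, for which no tabulation is stated anywhere.
- **That early termination goes unreported, weakening the primary answer.** Retention is in the primary endpoint, and Sections 3.1.3 and 4.6.1 give those who stop early particular follow-up. Section 6.2.4 does not cancel any of that. Only the breakdown by reason is missing.

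The defence does not close the gap. The Section 8.2 summary covers only events judged notable, names no denominator, is addressed to the IRB, and commits to no study result. Small N makes a description imprecise, not inapplicable.

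**Conclusion.** The point holds as an invalid reason, an internal contradiction and a reporting gap. Section 6.2.4 and the synopsis conflict with Section 5.4. No AE or SAE summary is planned as a study result, early terminations are not tabulated by reason, and alert-value referrals are counted nowhere.

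The impact is modest: the study is small, is described as minimal risk, has IRB-level AE reporting, and measures retention in its primary endpoint. The documents do not show that a safety signal would be missed, and this point does not claim so. The intervals assume all eight planned participants enrol. Section 3.3.2 allows enrolment to end sooner, and for no events the upper limit would then be higher.

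**What to change.** Replace the text of Section 6.2.4 with:

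> AEs and SAEs (events and participants affected), early terminations with reason, and alert-value referrals (baseline and final visits shown separately) will be listed by participant and summarised as n/N. Exact 95% confidence intervals may be shown for on-study events. No comparison is made.

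The two visits must be separated because, under Table 1, the baseline visit precedes the first coaching session. Pooling would mix pre-existing findings with on-study ones. The intervals are optional, since the rest of Section 6.2 uses plain descriptive summaries.

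Replace the synopsis entry for Safety Evaluations with a reference to Section 5.4, and check that the synopsis and Sections 5.4, 6.2.4 and 8.2 then agree.

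The cost is a short paragraph, one cross-reference and one table. AE forms and biometric values are already to be collected (Sections 8.2 and 6.1). The number of referrals may need one extra field, because Section 8.4 does not clearly say where an alert page is logged. The downside is the imprecision shown above, which the report should state so that zero events is not taken as reassurance.

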6.3 Sample Size and Power

This sample size is appropriate for the goal of treatment development and protocol refinement. This is in line with ongoing studies by [name] (HSR#17-4351) as well as the current literature.¹¹⁰

7 STUDY MEDICATION

Participants who choose to work on quitting smoking with their coach will be provided with nicotine lozenges or patches. They will work closely with [name] on dosages and will follow the CV-Homes safety protocol if participants mention adverse reactions. The study team will provide the first supply of Nicorette lozenges or patches up to \$20 in value. Then, the PI or coach will work to support the patient in connecting with other sources of lozenges or patches through options such as their clinic, Health Care for the Homeless, or Quit Partner MN.

8 SAFETY MANAGEMENT

8.1 Clinical Adverse Events

Clinical adverse events (AEs) and serious adverse events (SAEs) will be closely monitored throughout the study in accordance with HHRI IRB definitions and policies.

8.2 Adverse Event Reporting

Unanticipated problems related to the research involving risks to participants or others that occur during this study and SAEs will be reported to the IRB in accordance with IRB Prompt Reporting Guidelines. AEs that are not serious but that are notable and could involve risks to Participants will be summarized and submitted to the IRB at the time of continuing review.

[name] will be responsible for completing Adverse Events Forms should an event occur. She will report Serious Adverse Events to the HHRI IRB within 24 hours of having received notice of the event.

[name] will collaboratively gather any information needed to investigate the event and determine subsequent action. Any subsequent action will be documented and reported to the HHRI IRB and/or C2DREAM grant leaders and/or the Program Officer at NIH.

Adverse event reports will be reviewed annually with the HHRI IRB to ensure participant safety.

8.3 Investigator Reporting of a Serious Adverse Event to Sponsor

Reporting to the National Institutes of Health will be completed as required by their policies or advised by HHRI IRB staff.

8.4 Medical Emergencies

If non-urgent psychological distress arises in participants during study related activities, study staff will provide a handout about local mental health resources, including a 24-hour support line, behavioral health walk-in center, and psychiatric emergency room. If non-urgent physical health needs arise in participants, study staff will provide written resources about health care available through Health Care for the Homeless and Hennepin Healthcare. If staff identify that a participant has a high A1c or high cholesterol level, they will encourage the participant to visit their primary care physician or provide a resource sheet so that the participant can select a clinic to visit. If a participant wants to use nicotine patches to quit smoking, coaches will educate the participant on proper use of the patch and symptoms to be aware of such as skin irritation, dizziness, rapid heartbeat, or upset stomach that may arise if a person smokes while using the patch. Coaches will

encourage participants to reach out to their primary care provider or regular clinic prior to using the patch if they have any concerns or significant comorbidities and if they experience symptoms such as chest pain or if they become pregnant.

If an emergency physical or behavioral health situation arises, study staff will arrange for immediate clinical support from PI ([name]), Health Care for the Homeless clinical staff (who have a walk-in treatment model), the Hennepin County mental health crisis team (COPE Line, available by phone or in-person 24hrs./day, 7 days/week), or emergency medical services as appropriate. In the case of suicidal ideation, study staff will use the SI Questionnaire to guide their approach to working with the participant and reach out to [name] for support. These events will be written up and reviewed by the PI ([name]) and primary mentor ([name]) within 48 hours of the event and reported to the IRB if needed.

If measured blood pressure surpasses SBP>180 or DBP>100 or pulse>150 or if blood sugar measurement takes place within a study visit and falls <60 or >400/error, study staff will page [name] who will provide clinical assessment of symptoms and make referral or arrangement for immediate transfer to appropriate treatment as needed.

As deemed necessary by the primary mentor and/or HHRI IRB, issues related to patient safety will be reviewed with mental health or medical professionals at HCMC not affiliated with the study who will provide recommendations for withdrawal from the study, referrals for additional care, or other necessary action.

9 STUDY ADMINISTRATION

9.1 TREATMENT ASSIGNMENT METHODS

9.1.1 Randomization or Other Assignment *No randomization will occur in this single arm trial.*

9.1.2 Blinding *There will be no blinding.*

9.1.3 Unblinding *Not applicable*

9.2 Data Collection and Management

We will assign study ID numbers to all participants. Study IDs will be used on all study documents. Consent forms will be stored separately and will not be associated with study IDs when stored. Tracking forms will ensure each enrolled participant has a completed consent form.

Data from paper surveys administered during screening interviews and assessment visits will be entered and stored in REDCap. Physical copies of the surveys will be stored in a locked file drawer separate from consent documents. Electronic health record access will take place in Hennepin Healthcare EPIC or via faxed paper copies of medical records from other health systems.

All treatment sessions and post-treatment interviews will be audio recorded. Notes about treatment plans and notes summarizing main themes about satisfaction, treatment experience, and suggested changes will be created. Notes will remove all 18 HIPPA personal identifiers if mentioned. Notes will use only Participant ID numbers and will contain no personal identifiers. Once audio recordings are uploaded to the HHRI-maintained computer network, they will be

deleted from the audio recording equipment. Audio recordings will be destroyed on or before the end of the study, 10/31/2024.

Since assessment visits will be conducted at locations away from the research offices, research staff will store all documents in a locked folder while moving between community locations and the office. Immediately after visits, consent forms, point of care test results, audio equipment, and other study materials will be returned to the secure research offices of Hennepin Healthcare Research Institute. Each office has a locked door in a badge-access-only wing of the Institute. Signed consent documents will further be stored in a locked file drawer whose key will be stored in a separate locked key box.

Study data, including all audio recordings will be stored and analyzed on [name] and her staff's HHRI-maintained computer network. This network is robust, secure, and has state-of-the-art back-up and password protections. [name] and staff will comply with any necessary software, hardware, and data storage updates to maintain the security of this system under the direction of the HHRI IT Department.

